1.0 Research Design

1.1 Purpose/Specific Aims

The purpose of the research is to investigate the relationship between TSK scores and single-leg balance test results in ACL reconstruction patients.

A. Objectives

This study aims to answer the following questions:

- 1.) Is there a significant difference in single-leg balance between those with kinesiophobia and those without?
- 2.) Is there a change in kinesiophobia and single-leg balance test results over time?

B. Hypotheses / Research Question(s)

This study's hypothesis is that patients who score higher on the TSK (more fear) will do worse on the single-leg balance test than patients who score lower on the TSK.

1.2 Research Significance

The proposed research holds significant implications for advancing our understanding of the impact of kinesiophobia on the recovery outcomes of patients undergoing ACL reconstruction. While existing literature establishes a connection between kinesiophobia and suboptimal recovery, this study seeks to fill a critical gap by investigating the unexplored relationship between kinesiophobia, as measured by the Tampa Scale of Kinesiophobia (TSK), and single-leg balance in ACL reconstruction patients. By employing the TSK, a widely recognized and validated measure of kinesiophobia, and incorporating a single-leg balance test, this research aims to uncover potential correlations that could enhance our ability to predict and address challenges in rehabilitation. The hypothesized association between higher TSK scores and poorer performance on the single-leg balance test introduces a novel dimension to the field, offering insights that can inform targeted interventions and contribute valuable data to the sports medicine literature. This investigation aligns with ethical considerations as it seeks to improve the overall well-being and quality of life for orthopedic patients by refining rehabilitation strategies based on a more comprehensive understanding of kinesiophobia's impact on functional outcomes.

1.3 Research Design and Methods

This study is a randomized prospective study.

A. Research Procedures

The research procedures for this project will involve a comprehensive assessment of kinesiophobia using the Tampa Scale of Kinesiophobia (TSK) at both pre-operative and post-operative time points, specifically at 3 months, 6 months, and 1 year after ACL reconstruction. This will provide insights into the evolution of kinesiophobia throughout the critical phases of recovery. Additionally, the study aims to investigate the relationship between kinesiophobia and single-leg balance. The single-leg balance tests will be conducted in a trial of three, with a step in between each trial, to ensure a robust evaluation of participants' balance abilities. The time taken to touchdown during the single-leg balance tests will be measured. These assessments will be performed at 3 months, 6 months, 9 months, and 1 year post-operatively. Importantly, the balance assessments will be conducted on both the right and

left sides, allowing for a detailed comparison and analysis of potential asymmetries in balance recovery between the two limbs.

At the 6-month mark, all participants will undergo a functional evaluation by a physical therapist, including a single-leg hop test, triple hop test, triple cross-over test, and a timed 20m hop on a single leg. These functional tests are designed to provide additional insights into the participants' overall recovery and functional capabilities. Furthermore, strength testing will be conducted using the MicroFET device, with a focus on quadriceps and hamstrings at a 90-degree joint angle, as well as assessments of hip flexion, hip extension at full extension, and hip adduction. This comprehensive grouping of assessments at the 6-month milestone will contribute valuable data to the study, enhancing our understanding of the interrelationships between kinesiophobia, single-leg balance, functional performance, and muscle strength during the critical rehabilitation period following ACL reconstruction.

All information will be logged into Red Cap.

B. Data Points

TSK and single leg balance on both sides will be measured by approved physical therapists.

C. Study Duration

The study is expected to collect and analyze data for 1-2 years.

D. Endpoints

Primary endpoints:

- TSK
- Single Leg Balance
- Strength as measured by MicroFET

Secondary endpoints:

- KOOS Jr.

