1.6 Study Variables

A. Independent Variables, Interventions, or Predictor Variables

The independent variable in this study is the multifaceted assessment, spanning kinesiophobia levels using the Tampa Scale of Kinesiophobia (TSK), single-leg balance performance, and strength measurements, including quadriceps and hamstrings strength at a 90-degree joint angle and hip strength. These measures collectively serve as key predictors and interventions, capturing the complex dynamics of recovery following ACL reconstruction.

B. Dependent Variables or Outcome Measures

Outcome measures recorded for this study include the evolution of kinesiophobia levels measured by the Tampa Scale of Kinesiophobia (TSK) at pre-operative and post-operative time points (3, 6, and 12 months), single-leg balance performance measured through time-to-touchdown assessments at corresponding intervals, and quantitative data on strength measurements, encompassing quadriceps and hamstrings strength at a 90-degree joint angle, as well as strength assessments for hip flexion, hip extension at full extension, and hip adduction. Additionally, a comprehensive functional evaluation at 6 months includes the Single-Leg Hop Test, Triple Hop Test, Triple Crossover Test, and the timed 20m Hop on a Single Leg.

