6.0 Data Management Plan

6.1 Data Analysis

Data will be analyzed using correlation testing—to test results at each time point—and longitudinal model—to show if there is a potential time effect on the results. Mean single-leg balance will be compared between time points based on whether the patient is diagnosed with kinesiophobia using a t-test. Power analysis via comparison to existing baseline values in the relevant literature was done to determine the number of participants required for a well-powered study.

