6.4 Reporting Results

A. Individual Subjects' Results

Results of the study will be available to study participants at the conclusion of the study.

Therapists will discuss results of individual balance and functional testing with patients at completion of the testing.

B. Aggregate Results

Aggregate results will be available at the conclusion of the study for all participants.

C. Professional Reporting

Study results will be statistically analyzed and results compiled into a formal article which will be submitted for presentation/publication.

D. Clinical Trials Registration, Results Reporting and Consent Posting

NA

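### Section 1.3 calls the study randomized, but the protocol describes a single observational cohort compared by measured kinesiophobia status, so its results can support association only

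*Protocol*

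**What the plan says.** The design is stated once, at the start of Protocol section 1.3: "This study is a randomized prospective study". Section 1.6 A, on the independent variables, says of the TSK, balance and strength assessments: "These measures collectively serve as key predictors and interventions".

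The comparison of interest is set by the first objective in section 1.1: "Is there a significant difference in single-leg balance between those with kinesiophobia and those without". Section 6.1 plans three analyses: correlations at each time point, a longitudinal model for change over time, and a comparison of mean balance "based on whether the patient is diagnosed with kinesiophobia using a t-test".

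Section 1.2 describes the purpose partly in terms of correlation and association, and partly as advancing "understanding of the impact of kinesiophobia on the recovery outcomes of patients undergoing ACL reconstruction".

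**The concern.** Randomization is a specific property. Chance, and not the patient's history or condition, decides who is in which group, so the groups differ at the outset only by chance. A reader who meets the word in the design sentence will assume that the main contrast has this protection.

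Here the contrast is between patients with more and less fear of movement. Patients are not assigned to fear. They bring it with them, together with whatever else goes with it. Two explanations other than an effect of fear then stay open:

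- **Confounding.** A common cause, such as a worse injury or more pain, could raise the TSK score and also shorten the time to touchdown.
- **Reverse causation.** A patient whose balance is poor may become more fearful for that reason. Correlations taken at the same visit cannot separate the two directions.

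At stake is the kind of conclusion the study can support. A difference in balance by kinesiophobia status would be an association. Under a randomized label it could be taken for an effect.

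**Working it through.** No arithmetic applies, because the point depends on no figure. The check is to go through each section where a randomized design would have to leave a trace and see what is there.

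| Protocol section | What randomization would require | What the section contains |
|---|---|---|
| 1.1 Aims | A comparison between assigned groups | A comparison of patients with and without kinesiophobia, and change over time |
| 1.3 A Procedures | Procedures that differ by arm | One set of assessments; the 6-month functional evaluation applies to everyone |
| 1.5 and 4.3 Sample size | Number per arm or allocation ratio | One total, 25, inflated by 10% for drop-out |
| 1.6 A Independent variables | An assigned factor | TSK, balance and strength measurements |
| 1.6 B Outcomes | Outcomes distinct from the assigned factor | TSK, balance and strength again, plus the functional tests |
| 1.7 and 1.8 Data collection, schedule | A randomization step after enrolment | Enrolment before surgery, then the same questionnaires and tests for all |
| 4.1 Enrolment | Assignment after screening | Identification, recruitment and screening only |
| 4.4 Consent | Disclosure of the possible arms | The only alternative presented is not to take part |
| 6.1 Analysis | A comparison by allocated arm | Correlation, a longitudinal model, and a t-test by kinesiophobia diagnosis |

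Three things follow.

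1. No section has arms, a ratio, a random sequence or an assigned treatment. The design sentence in 1.3 is the only mention of randomization.
2. None of the three analyses in 6.1 uses an allocated group. The grouping variable is a measured characteristic of the patient, which cannot be allocated.
3. The items that 1.6 A calls interventions are measurements. Section 1.6 B lists TSK, balance and strength as outcomes too, so they cannot be treatments whose effect is being tested.

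The design sentence and the rest of the protocol cannot both be right. Since aims, procedures, sample size, schedule, enrolment, consent and analysis agree with each other, the design sentence is the one in error.

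**The case against.** **One word, possibly template residue.** The aims speak of a relationship, section 1.2 of correlations and a hypothesized association, and section 6.1 of correlation testing. No analysis or sample-size statement relies on randomization. All of this stands, and it lowers the severity. It does not make the sentence true, and that sentence is where a reader looks for the study type.

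**The word *interventions* in 1.6 A echoes the heading of that subsection.** This also stands. It is loose wording and not a second, independent contradiction. It is worth removing because it leans the same way as the error in 1.3.

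**An allocation might be described elsewhere.** The text checked lacks some material before section 1.0, between 1.8 and 2.2, and between 2.3 and 3.0, and a separate SAP may exist. Neither helps. The sections that would have to carry an allocation are all present and carry none, and a SAP cannot create one.

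**Stronger readings that the documents do not support.**

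- A reader might infer that the protocol sets out to prove that fear causes poor balance. It does not: there is no formal causal hypothesis, and the *impact* wording sits in background prose beside associational wording.
- A reader might want to attach a false-positive rate to the confounding. The protocol gives no correlations from which to compute one. Any such rate would apply equally to every observational cohort of 25 and would be the same after the word is deleted, so it does not measure this error.
- A reader might see a conflict with section 6.4 D, where registration is marked as not applicable. That entry sits awkwardly only with the wrong label. Whether registration is required depends on rules outside the documents.
- A reader might suppose that the label has sent the study down the wrong review or reporting route. No section shows the label driving any such decision; section 6.3 B, for example, justifies the absence of a monitoring board by small numbers.

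**Conclusion.** The point holds as a misstatement of the design. Section 1.3 claims randomization, and the study described is a prospective single-cohort observational study in which the main contrast is by measured kinesiophobia status. That contrast is exposed to confounding and reverse causation, and its results can be read only as associations.

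Severity is moderate. No estimate, test, sample size or procedure changes. What changes is the stated strength of the evidence and hence what may be concluded. The size of any bias cannot be given from the documents, and the verdict does not depend on it. It rests on one assumption: that the enrolment, schedule, consent and analysis sections describe the study as it will be run.

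**What to change.** 1. In section 1.3, replace the design sentence with: *This is a prospective, single-cohort observational study; no participant is randomized and no intervention is assigned.*
2. In section 1.6 A, delete the words *and interventions*, so that the measurements are described as predictors only.
3. In section 6.1, add a sentence saying that the comparison by kinesiophobia status and the correlations are interpreted as associations and not as effects of kinesiophobia, and that the *impact* wording in section 1.2 is to be read in that sense.

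The cost is a wording amendment. It needs no new data, participants, visits or analyses. The stated design will look weaker than it does now, but it will match the study being run.

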1.4 Preliminary Data

Preliminary TSK data was used for power analyses; this data will not be used for the actual study.

1.5 Sample Size Justification

The targeted sample size for this study is established at N=25, with a 10% inflation to accommodate potential dropouts. Participants undergoing ACL surgery will be recruited from UOA Somerset, Wall, Avenel, and Morganville locations.

Based on our sample size software and utilizing the preliminary data and relevant literature, the maximum number of patients needed to detect the difference in means (of the preliminary data and of similar studies in the literature) is around 5 people. For a true pilot study, we will target around 20-25 people, and then inflate for ~10% drop-out.

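### The sample-size basis is a comparison of preliminary TSK data with literature values, which is none of the planned analyses, so the power of N=25 for Objective 1 and the hypothesis is not established

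*Protocol*

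**What the plan says.** Three sections of the protocol describe the sample-size basis.

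- Section 1.4: "Preliminary TSK data was used for power analyses; this data will not be used for the actual study".
- Section 1.5 reports the result of the calculation, as an upper limit for recruitment: "needed to detect the difference in means (of the preliminary data and of similar studies in the literature) is around 5 people". It then sets the target on a different ground: "For a true pilot study, we will target around 20-25 people, and then inflate for ~10% drop-out". The same section fixes the target at N=25 plus 10% for dropout.
- Section 6.1: "Power analysis via comparison to existing baseline values in the relevant literature was done to determine the number of participants required for a well-powered study".

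Section 6.1 also gives the planned analyses. One sentence plans correlation testing at each time point and a longitudinal model for a time effect. The next reads: "Mean single-leg balance will be compared between time points based on whether the patient is diagnosed with kinesiophobia using a t-test".

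Section 1.1 sets out what these analyses must answer. Objective 1 is a difference in single-leg balance between patients with and without kinesiophobia. Objective 2 is change over time in kinesiophobia and in balance. The hypothesis is that higher TSK scores go with worse balance.

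**The concern.** The protocol's sample-size reasoning answers a question the study does not ask. Comparing a set of TSK scores with published values gives no information about how balance differs by kinesiophobia status, how variable balance times are, how patients will split between the two groups, or how strongly TSK and balance are correlated. The protocol reports none of these quantities.

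The two descriptions of the study also pull apart. Section 6.1 says a power analysis set the number for a well-powered study. Section 1.5 takes 20 to 25 from a pilot convention, four to five times the calculated figure and not derived from it.

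What is at stake is how a null result would be read. Section 6.4 plans publication. If the protocol says about five patients are enough, a non-significant result in 25 could be presented as good evidence of no relationship, when the interval could still contain correlations of practical interest.

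**Working it through.** **1. The powered comparison against the planned ones**

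| | Variable | Comparison |
|---|---|---|
| Power analysis (1.4, 1.5, 6.1) | TSK (the only preliminary data named) | Preliminary data vs literature values |
| t-test (6.1, Objective 1) | Single-leg balance | Kinesiophobia vs none |
| Correlation (6.1, hypothesis) | TSK and balance | Association at each time point |
| Longitudinal model (6.1, Objective 2) | TSK and balance | Change over time in the same patients |

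The first row matches none of the others.

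**2. The protocol's own figure**

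The figure of about five cannot be reproduced. No alpha, power, mean difference or SD is given, nor whether five is a total or per group. One can only solve for the effect it implies. Assumptions: alpha 0.05, 80% power, noncentral t.

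| Reading of n=5 | d, two-sided | d, one-sided |
|---|---|---|
| One sample of 5 (or 5 pairs) | 1.68 | 1.36 |
| 5 per group | 2.02 | 1.72 |
| 5 in total, split 2/3 | 3.89 | 3.01 |

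The one-sample reading is the closest to comparing a sample with published values. A correlation tested on five people would need |r| of about 0.93 to 0.94 (simulated power 78% and 82%). On every reading, five suffices only for a very large effect.

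**3. What N=25 detects in the planned analyses**

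Inputs: 25 completers (sections 1.5 and 4.3). Assumed: two-sided alpha 0.05, 80% power, and group splits of 12/13 and 5/20 as a range, since kinesiophobia prevalence is not given.

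*Balance t-test.* Noncentrality = d × √(n1·n2/(n1+n2)), with 23 degrees of freedom.
- 12/13: √(156/25) = 2.50; 80% power at d = 1.17.
- 5/20: √(100/25) = 2.00; 80% power at d = 1.46.
- Power at 12/13: 22% for d = 0.5 and 48% for d = 0.8.

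*Correlation.* Fisher z: |r| = tanh((1.960 + 0.842)/√(25−3)) = tanh(0.597) = 0.535. Simulation from a bivariate normal gives 80% power at about 0.53. Power for r = 0.3: Φ(0.3095 × √22 − 1.960) = Φ(−0.508) = 31%.

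*Within-patient change (Objective 2).* A paired t-test on 25 pairs has 24 degrees of freedom and noncentrality d × √25; 80% power at a standardized change of about 0.58.

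*One-sided alternative*, since the hypothesis is directional: d = 1.03 (12/13) or |r| of about 0.48.

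**4. What N=25 estimates**

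Half-width on the Fisher z scale: 1.960/√22 = 0.418.
- Observed r = 0.3: tanh(0.310 ∓ 0.418) gives a 95% CI of −0.11 to 0.62.
- Observed r = 0: tanh(±0.418) gives about ±0.40.

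**5. Dropout**

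25/0.9 and 25 × 1.1 both round up to 28, so the inflation is not at issue.

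**The case against.** The strongest reply is that inadequate power is not shown. The protocol gives no numeric power, effect size or SD, and N=25 is a pilot target, not the output of the calculation. If the true effect were about d=1.2 with a near-even split, or r=0.53, 25 would be enough. This stands. A reader might infer that N=25 falls short of a stated power, but there is no stated figure to fall short of. The documents support only that power for these analyses is not established.

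A second reply is that TSK is not foreign to the study: it is a primary endpoint, and Objective 2 asks about its change over time. This stands in part. Within-patient change is where 25 does best, at about 0.58 SD. But comparison with published values is not within-patient change, so the calculation does not support Objective 2 either.

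Third, sections 1.5 and 6.1 do not name the literature variable, and the word maximum may mean several calculations were run. Also fair: one can say that no balance input is reported, not that none was used.

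A further tempting inference is that a null result in 25 patients could exclude only very large effects. That confuses the detectable effect with what an interval excludes. An observed r of 0 would exclude correlations beyond about ±0.40, tighter than the detectable 0.53.

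**Conclusion.** The point holds in limited form. The reported sample-size basis does not correspond to the balance t-test, the correlation or the longitudinal model, so neither the five-person figure nor the well-powered claim supports them, and that claim conflicts with the pilot description. This is a mismatch between justification and analysis; no arithmetic error is shown.

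For Objective 1 and the hypothesis, N=25 has 80% power only for large effects (d of about 1.17 to 1.46 depending on the split, or |r| of about 0.53) and low power for moderate ones. These figures rest on an assumed two-sided alpha of 0.05, assumed 80% power, assumed splits and 25 completers; one-sided testing lowers the thresholds without changing the conclusion. Nothing here shows that 25 is the wrong size for a pilot.

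**What to change.** Keep N=25. In section 1.5 delete the five-person figure, and in section 6.1 delete the well-powered claim. Replace them with a pilot justification, labelling alpha, power and group split as assumptions:

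- With 25 completers, two-sided alpha 0.05 and 80% power, the study detects a standardized balance difference of about 1.17 (12/13 split) to 1.46 (5/20 split), a correlation of about 0.53, or a standardized within-patient change of about 0.58.
- Expected precision: an observed r of 0.3 would have a 95% CI of about −0.11 to 0.62, and an observed r of 0 about ±0.40.
- A non-significant result will not be read as evidence of no association.

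If the sponsor prefers to keep a power claim, it should rest on the balance difference or the TSK-balance correlation, with alpha, power, SD and expected split stated.

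The cost is rewording in two sections. No patients, endpoints or analyses change. The downside is that the stated figure becomes less favourable.

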1.6 Study Variables

A. Independent Variables, Interventions, or Predictor Variables

The independent variable in this study is the multifaceted assessment, spanning kinesiophobia levels using the Tampa Scale of Kinesiophobia (TSK), single-leg balance performance, and strength measurements, including quadriceps and hamstrings strength at a 90-degree joint angle and hip strength. These measures collectively serve as key predictors and interventions, capturing the complex dynamics of recovery following ACL reconstruction.

B. Dependent Variables or Outcome Measures

Outcome measures recorded for this study include the evolution of kinesiophobia levels measured by the Tampa Scale of Kinesiophobia (TSK) at pre-operative and post-operative time points (3, 6, and 12 months), single-leg balance performance measured through time-to-touchdown assessments at corresponding intervals, and quantitative data on strength measurements, encompassing quadriceps and hamstrings strength at a 90-degree joint angle, as well as strength assessments for hip flexion, hip extension at full extension, and hip adduction. Additionally, a comprehensive functional evaluation at 6 months includes the Single-Leg Hop Test, Triple Hop Test, Triple Crossover Test, and the timed 20m Hop on a Single Leg.

